4.3.3.2 Defocus Curve Evaluation

Descriptive statistics (mean, median, standard deviation, number of eyes/subjects, minimum, maximum, and two-sided 95% confidence intervals) will be provided for the logMAR VA measured on the ETDRS chart at each defocus value (-2.50 D to -0.50 D in 0.50 D increments, -0.25 D to +0.25 D in 0.25 D increments, +0.50 D to +1.50 D in 0.50 D increments) for all eyes/subjects. The mean logMAR VA measured on the ETDRS chart at each defocus value will be displayed graphically for all eyes/subjects, separately for first implanted eye, second implanted eye and binocular assessments. Mean logMAR visual acuity will be plotted versus defocus value, including two-sided 95% confidence intervals and standard deviations, with the amount of defocus along the x-axis and logMAR VA at each defocus point along the y-axis. The defocus tables and plots will be generated overall and by site at Month 3/Visit 4A and Month 6/Visit 5A.

In addition, monocular defocus curves for the first implanted eye and second implanted eye will be presented, by IOL group, for the following three photopic pupil size ranges [<3.0 mm (small), ≥ 3.0 to ≤ 4.0 mm (medium), and >4.0 mm (large)] and three axial length ranges

[Redacted]

[Redacted]

[Redacted]

[Redacted]

[Redacted]

[Redacted]

[Redacted]

[Redacted]

[Redacted]

[Redacted]

[Redacted]

[Redacted]

[Redacted]

[Redacted]

[Redacted]

[Redacted]

[Redacted]

[Redacted]

[Redacted]

[Redacted]

[Redacted]

[Redacted]

[Redacted]

[Redacted]

[Redacted]

[figure not shown]
[Redacted]

4.3.3.8 Spectacle Use Questionnaire

[figure not shown]
Response to each question in spectacle use questionnaire will be summarized with descriptive statistics (number and percentages) by IOL group.

4.4 Multiplicity Strategy

Overall type I error will be maintained at 0.05 level for the Month 3/Visit 4A (70-100 day post 2nd eye implantation) analyses using the sequential testing approach summarized in the figure below.

The following primary and secondary effectiveness analyses will be performed on the Month 6/Visit 5A (120-180 day post 2nd eye implantation) data using the sequential testing approach summarized in the figure below if the primary and both secondary null hypotheses are rejected for the Month 3/Visit 4A (70-100 day post 2nd eye implantation) analysis. If any null hypothesis is not rejected, no further hypothesis testing will be performed.

4.5 Subgroup Analyses and Effect of Baseline Factors

Subgroup analyses of the primary and secondary visual acuity endpoints will be conducted to assess the consistency of treatment effect across various subgroups.

The consistency of the treatment effect for monocular DCIVA, monocular BCDVA and monocular DCNVA will be assessed descriptively using summary statistics by category of the following subgroup factors:

- Age category (<65 vs. ≥65 years)
- Site
- Adverse event (study eyes with ocular adverse events vs. study eyes without ocular adverse events) and
- Preoperative ocular pathology (study eyes with vs. study eyes without)

4.6 Handling of Missing Data

The AAS and BAS do not include any imputed values. Although the influence of missing data is expected to be minimal, the following sensitivity analyses will be conducted to assess the impact of missing data on the conclusions from the primary endpoint analysis.

1. Multiple imputation (with a fully conditional specification) method will be used to impute and estimate the treatment effect.
2. The sensitivity of inferences to departures from the MAR assumption will be examined using a pattern-mixture model approach (with a control-based pattern imputation^[4]).

Sensitivity Analysis 1:

A fully conditional specification (FCS) method will be used to impute missing DCIVA values at all visits in a data set with an arbitrary missing pattern. The FCS method uses a separate conditional distribution for each imputed variable.

The following SAS pseudo-code with the PROC MI procedure will be used to impute missing DCIVA values using FCS method:

```

/* multiple imputation w/ MAR assumption          */
/* DCIVA1-DCIVA4 should be in parallel structure */
proc mi data=mi_in seed=1001 nimpute=10 mu0=.3 .2 .1 .0 out=mi_out1;
  fcs nbiter=20 reg; *reg(/details);
  var DCIVA1 DCIVA2 DCIVA3 DCIVA4;
run;

/* run glm on each iteration of mi */
proc glm data=mi_out1;
  by _Imputation_;
  class LENS_MODEL;
  model DCIVA4 = LENS_MODEL;
  estimate 'Trt_Eff' LENS_MODEL 1 -1;
  ods output Estimates = glm_out1;
run;

/* no need to sort if there is only one parameter being estimated */

```

```

proc sort data=glm_out1;
  by parameter _imputation_;
run;

/* generate estimates and CIs from multiple imputation */
proc mianalyze data=glm_out1;
  by parameter;
  modeleffects estimate;
  stderr stderr;
  ods output ParameterEstimates = Param_out1;
run;

```

Sensitivity Analysis 2:

The sensitivity of inferences to departures from the MAR assumption will be examined using a pattern-mixture model approach with a control-based pattern imputation.

The following SAS pseudo-code with the PROC MI procedure will be used to implement the control-based pattern imputation:

```

/* multiple imputation w/ MNAR assumption */
/* DCIVA1-DCIVA4 should be in parallel structure */
proc mi data=mi_in seed=1001 nimpute=10 mu0=.3 .2 .1 .0 out=mi_out2;
  class LENS_MODEL;
  fcs nbiter=20 reg; *reg(/details);
  mnar model( DCIVA1 DCIVA2 DCIVA3 DCIVA4 /modelobs=(LENS_MODEL='SN60WF'));
  var DCIVA1 DCIVA2 DCIVA3 DCIVA4;
run;

/* run glm on each iteration of mi */
proc glm data=mi_out2;
  by _Imputation_;
  class LENS_MODEL;
  model DCIVA4 = LENS_MODEL;
  estimate 'Trt_Eff' LENS_MODEL 1 -1;
  ods output Estimates = glm_out2;
run;

/* no need to sort if there is only one parameter being estimated */
proc sort data=glm_out2;
  by parameter _imputation_;
run;

/* generate estimates and CIs from multiple imputation */
proc mianalyze data=glm_out2;
  by parameter;
  modeleffects estimate;
  stderr stderr;
  ods output ParameterEstimates = Param_out2;
run;

```

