5 SCHEDULE OF PROCEDURES AND ASSESSMENTS

Visit	Visit 0 Pre- Op	Visit 00 OP ¹	Visit 1	Visit 2	Visit 00A: OP ²	Visit 1A	Visit 2A	Visit 3A	Visit 4A ³	Visit 5A ³	Early Exit
Eye	Both Eyes	1 st Eye	1 st Eye	1 st Eye	2 nd Eye	2 nd Eye	2 nd Eye	Both Eyes	Both Eyes	Both Eyes	
Day Number	Day -28-0	Surgery	Day 1-2	Day 7-14	Surgery	Day 1-2	Day 7-14	Day 30-60	Day 70- 100	Day 120- 180	N/A
Informed Consent	X										
Demographics	X										
Medical History	X										
Concomitant Medications	X	X	X	X	X	X	X	X	X	X	X
Inclusion/Exclusion	X	X			X						
Urine Pregnancy Test ⁴	X										
[REDACTED]	X										
[REDACTED]	X										
[REDACTED]	X										
[REDACTED]	X										
[REDACTED]	X										
[REDACTED]	X										
Spectacle Use Questionnaire										X	X
Distance VA at 4 m											
• [REDACTED]	X		X	X		X	X	X	X	X ⁵	X
• Photopic corrected	X		X	X		X	X	X	X	X ⁵	X
Intermediate VA at 66 cm											
• [REDACTED]								X	X	X ⁵	
• Photopic Distance Corrected								X	X	X ⁵	
Near VA at 40 cm											
• [REDACTED]									X	X ⁵	
• Photopic Distance Corrected									X	X ⁵	
Defocus Curve (4 m)									X ⁵	X ⁵	
Contrast Sensitivity											
• Mesopic without Glare									X	X ⁵	
• Mesopic with Glare									X	X ⁵	
[REDACTED]									X	X ⁵	
[REDACTED]									X	X ⁵	
[REDACTED]									X	X ⁵	
[REDACTED]									X	X ⁵	
[REDACTED]									X	X ⁵	
Target Residual Refractive Error ⁶	X										
[REDACTED]	X		X	X		X	X	X	X	X	X
[REDACTED]	X		X	X		X	X	X	X	X	X
[REDACTED]	X		X	X		X	X	X	X	X	X
[REDACTED]	X		X	X		X	X	X	X	X	X

Visit	Visit 0 Pre-Op	Visit 00 OP ¹	Visit 1	Visit 2	Visit 00A: OP ²	Visit 1A	Visit 2A	Visit 3A	Visit 4A ³	Visit 5A ³	Early Exit
Eye	Both Eyes	1 st Eye	1 st Eye	1 st Eye	2 nd Eye	2 nd Eye	2 nd Eye	Both Eyes	Both Eyes	Both Eyes	
Day Number	Day -28-0	Surgery	Day 1-2	Day 7-14	Surgery	Day 1-2	Day 7-14	Day 30-60	Day 70- 100	Day 120- 180	N/A
Operative Eye		X			X						
██████████		X			X						
Incision Location ⁷		X			X						
Final Incision Size ⁷		X			X						
██████████		X			X						
██████████			X	X		X	X	X	X	X	X
██████████			X	X		X	X	X	X	X	X
Adverse Events	X	X	X	X	X	X	X	X	X	X	X
Secondary Surgical Interventions		X	X	X	X	X	X	X	X	X	X
Device Deficiencies		X	X	X	X	X	X	X	X	X	X

¹ Visit 00 (1st eye surgery) must occur within 28 calendar days from Pre-Operative Visit (Visit 0).

² Visit 00A (2nd eye surgery) must occur after a minimum of 7 calendar days and a maximum of 28 calendar days after Visit 00 (1st eye surgery).

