9 SUBJECT POPULATION

The study population consists of male and female subjects 22 years of age and older with a diagnosis of cataract in both eyes requiring surgery with implantation of a monofocal IOL in the capsular bag. It is aimed to randomize approximately 260 subjects in approximately 16 centers globally, with a target of approximately 16 subjects randomized per site. Site specific targets may be adjusted based on individual site capabilities. Enrollment projections are as follows:

- 260 subjects to be randomized (10% discontinuation rate is expected)
- 234 subjects to successfully complete the final study visit (Visit 5A)
 - 130 subjects in the Model DFT015 arm

- 104 subjects in the Model SN60WF arm

Check all entry criteria at Screening/Visit 0 and at both surgical visits (Visit 00, Visit 00A). If a subject is excluded post randomization and prior to 1st eye surgery (IOL does not come in contact with the eye), the subject should be discontinued from participation in the study. Refer to Section 11.11 Discontinued Subjects for further details.

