1. Record changes in medical/ocular history and ocular and non-ocular concomitant medications.

2. [REDACTED]

[REDACTED]

[REDACTED]

[REDACTED]

[REDACTED]

7. Record any adverse events including SSIs. Refer to Section 12 for further detail.

- 8. Record any device deficiencies. Refer to Section 12 for further detail.

11.4 1-Week Postoperative Visit (Visit 2/2A)

Visit 2: 7-14 Days Post 1st Eye Implantation, Monocular 1st Eye

Visit 2A: 7-14 Days Post 2nd Eye Implantation, Monocular 1st Eye

Below is a list of study procedures to be completed at Visit 2 and Visit 2A. It is recommended that procedures are performed in the order described below unless otherwise stated. All assessments must be documented in source documentation and eCRF (if applicable).

- 1. Record changes in medical/ocular history and ocular and non-ocular concomitant medications.

[Redacted]

- 1. Measure and record [Redacted] and BCDVA under photopic conditions at 4 m.
[Operative Eye Only, Monocular]

[Redacted]

[Redacted]

[Redacted]

[Redacted]

- 8. Record any adverse events including SSIs. Refer to Section 12 for further detail.
- 9. Record any device deficiencies. Refer to Section 12 for further detail.

11.5 1-Month Postoperative Visit (Visit 3A)

Visit 3A: 30-60 Days Post 2nd Eye Implantation, Bilateral

Below is a list of study procedures to be completed at Visit 3A. It is recommended that procedures are performed in the order described below unless otherwise stated. All assessments must be documented in source documentation and eCRF (if applicable).

- 1. Record changes in medical/ocular history and ocular and non-ocular concomitant medications.

[REDACTED]
[REDACTED].

- 3. Measure and record monocular [REDACTED] and BCDVA under photopic conditions at 4 m. [*Both Eyes, Bilateral*]

- 4. Measure and record monocular [REDACTED] and DCIVA under photopic conditions at 66 cm. [*Both Eyes, Bilateral*]

[REDACTED]
[REDACTED]

[REDACTED]
[REDACTED]

[REDACTED]
[REDACTED]

[REDACTED]
[REDACTED]

[REDACTED]

- 10. Record any adverse events including SSIs. Refer to Section 12 for further detail.

- 11. Record any device deficiencies. Refer to Section 12 for further detail.

11.6 3-Month Postoperative Visit (Visit 4A)

Visit 4A: 70-100 Days Post 2nd Eye Implantation, Bilateral

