4.3 Statistical Methods for Effectiveness Analyses

4.3.1 Primary Effectiveness Analyses

For the primary effectiveness analysis, treatment group comparison for photopic distance-corrected intermediate visual acuity will be made and the primary objective will be demonstrated if (one-sided) $P < 0.025$ from a two-sample t-test at Month 3/Visit 4A. The difference in means (ACRYSOF IQ EDF IOL – ACRYSOF IQ Monofocal IOL) and the

associated two-sided 95% confidence interval will be presented.

The following SAS pseudo code will be used for the primary analysis:

```
proc glm data=visual_acuity;
  where IMPLANT_EYE = 'First';
  class LENS_MODEL;
  model DCIVA4 = LENS_MODEL;
  estimate 'Trt_Eff' LENS_MODEL 1 -1;
  lsmeans LENS_MODEL / pdiff cl;
run;
```

Poolability of primary outcomes across sites will be assessed using a fixed effects model including main effects of treatment and site along with a treatment by site interaction effect. Subjects across sites will be considered poolable if the interaction effect is not significant at type I error of 0.15. If the interaction effect is significant, a mixed effects model will be used to estimate treatment effect. The following mixed effect models will be used and compared using Bayesian information criterion (BIC).

1. A fixed effect for treatment and random effects for site and site by treatment interaction
2. A fixed effect for treatment and random effect for site

The model with smaller BIC will be selected as the final model to estimate treatment effect^[1]. The SAS pseudo code for each of the above models are provided below.

Fixed effects model for assessing poolability:

```
proc mixed data=visual_acuity;
  where IMPLANT_EYE = 'First';
  class LENS_MODEL SITE;
  model DCIVA4 = LENS_MODEL | SITE /DDFM = satterth;
  lsmeans LENS_MODEL / pdiff cl;
  ods output Diffs= DIFF LSMeans= LSMEAN;
run;
```

Mixed effects model(s) for obtaining estimate of treatment effect in the presence of site by treatment interaction:

```
proc mixed data=visual_acuity;
  where IMPLANT_EYE = 'First';
  class LENS_MODEL SITE;
  model DCIVA4 = LENS_MODEL /DDFM = satterth;
  random SITE SITE*LENS_MODEL; *[OR] random SITE;
  lsmeans LENS_MODEL / pdiff cl;
  ods output Diffs= DIFF LSMeans= LSMEAN;
run;
```

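### The MAR imputation run leaves lens group out of its imputation model and then estimates the lens effect; both imputation runs also list DCIVA variables that appear to have no scheduled measurement

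*SAP*

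**What the plan says.** SAP 4.6 describes two sensitivity analyses for missing primary-endpoint data.

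- **Sensitivity Analysis 1** is fully conditional imputation. Its code comment reads "multiple imputation w/ MAR assumption". The imputation call is "proc mi data=mi_in seed=1001 nimpute=10 mu0=.3 .2 .1 .0 out=mi_out1", followed by an FCS statement and "var DCIVA1 DCIVA2 DCIVA3 DCIVA4". There is no CLASS or BY statement, and `LENS_MODEL` is not in VAR. The text says that missing DCIVA at all visits is imputed and names no treatment term. A GLM of DCIVA4 on `LENS_MODEL` is then fitted to each imputed data set.
- **Sensitivity Analysis 2** is the control-based run, meant to show sensitivity to departures from MAR. It declares `LENS_MODEL` as a class variable, but only so that imputation can be fitted to control observations. Its MNAR list starts "mnar model( DCIVA1 DCIVA2 DCIVA3 DCIVA4 /modelobs=(LENS_MODEL='SN60WF", so it repeats the same four variables.

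SAP 4.3.1 fits "model DCIVA4 = LENS_MODEL" for the primary test at Month 3/Visit 4A, so DCIVA4 is the Visit 4A value. In the Protocol 5 schedule, the photopic distance-corrected row under "Intermediate VA at 66 cm" is marked at Visits 3A, 4A and 5A only, and not at Early Exit. In Protocol 11, the first visit whose procedures include monocular testing of BCDVA at 4 m "and DCIVA under photopic conditions at 66 cm" is Visit 3A (Protocol 11.5).

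**The concern.** An imputation model should contain every term of the analysis model that follows. Here it omits the one term being estimated. Missing test-lens eyes are imputed partly from control-lens eyes, and the reverse, so the imputed values carry too little of the lens difference, or the wrong amount of it. The run is therefore not a valid MAR analysis even when its MAR assumption is true.

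This matters because the second run is meant to show what happens when MAR fails, and it needs an MAR result to be read against. If the first run is itself pulled to nearly the same place as the control-based run, their agreement looks like robustness but shows almost nothing.

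The variable list is a separate problem. A regression cannot be fitted for a variable with no observed values, so neither run can be carried out as printed. The change would have to be made during programming. Protocol 10.4 has designated personnel unmasked at the interim lock, so it is better specified before then.

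**Working it through.** **Inputs from the documents.** Planned DCIVA difference d4 = -0.12 logMAR, SD s = 0.18, one-sided 0.025, 130 and 104 completers, 260 randomized 5:4 (SAP 7). That gives 144 and 116 randomized, so the test share is p = 144/260 = 0.554 and p(1-p) = 0.247.

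**The plan's own figure.** With 130 and 104 subjects, power for -0.12 is 0.9991 (normal) or 0.9990 (noncentral t). This agrees with the stated >99%.

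**Assumptions, because the documents give no values.** The missing fraction f at Visit 4A is equal in both arms and unrelated to outcome within arm; the within-arm correlation between Visits 3A and 4A is rho; the Visit 3A effect is d3; the SD is the same at both visits. The figures show the effect of the missing treatment term using measured visits only. They are not the expected output of the code as printed.

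**Case 1: missing subjects have no other DCIVA.** This applies to an eye that leaves before Visit 3A. With the control mean set to 0, the pooled observed mean is p·d4, and missing values in both arms are drawn around it.

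- Test mean: (1-f)·d4 + f·p·d4. Control mean: f·p·d4.
- Difference: d4·(1-f).
- f = 2%, 5%, 10%: -0.1176, -0.1140, -0.1080.

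Control-based imputation has the same expectation, d4·(1-f).

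**Case 2: Visit 3A observed.** The pooled slope is b = [rho·s² + p(1-p)·d3·d4] / [s² + p(1-p)·d3²]. Imputed values differ between arms by b·d3, so:

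- pooled run = d4(1-f) + f·b·d3
- control-based run = d4(1-f) + f·rho·d3

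For d3 = -0.12 and rho = 0.3, b = (0.00972 + 0.00356)/(0.0324 + 0.00356) = 0.369. For rho = 0.5 and 0.7, b = 0.549 and 0.730.

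| f | Pooled, rho 0.3 | Pooled, rho 0.7 |
|---|---|---|
| 2% | -0.1185 | -0.1194 |
| 5% | -0.1162 | -0.1184 |
| 10% | -0.1124 | -0.1168 |

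At f = 10% the control-based run gives -0.1116, -0.1140 and -0.1164 for rho = 0.3, 0.5 and 0.7.

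**Direction.** Setting b·d3 = d4 reduces to d3 = d4/rho, which is -0.40, -0.24 and -0.171 for rho = 0.3, 0.5 and 0.7. Beyond that point the bias is away from zero: at f = 10% and rho = 0.7, d3 = -0.18 gives -0.1205 and d3 = -0.20 gives -0.1215.

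**Gap between the two runs.** Over f 2-10%, rho 0.3-0.7 and d3 from -0.06 to -0.20, the largest gap is 0.0014 (f = 10%, rho = 0.3, d3 = -0.20: -0.1154 against -0.1140).

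**Simulation check** (Visits 3A and 4A only, 2,000 trials, 10 imputations, 144/116 eyes). The table shows the mean pooled estimate minus the mean estimate from imputation within arm.

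| Scenario | Simulated | Closed form |
|---|---|---|
| f = 10%, no Visit 3A | +0.0120 | +0.0120 |
| f = 10%, rho 0.5, d3 = -0.12 | +0.0054 | +0.0054 |
| f = 10%, rho 0.7, d3 = -0.12 | +0.0031 | +0.0032 |
| f = 10%, rho 0.7, d3 = -0.20 | -0.0016 | -0.0015 |
| f = 5%, no Visit 3A | +0.0060 | +0.0060 |
| f = 5%, rho 0.5, d3 = -0.12 | +0.0027 | +0.0027 |

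The Monte Carlo SE is at most 0.00011. Imputation within arm matched the unimputed t-test within 0.0002 throughout.

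**Variable list.** If DCIVA4 is Visit 4A, DCIVA3 is naturally Visit 3A, and DCIVA1 and DCIVA2 would be the earlier visits, where 66 cm acuity is not scheduled. The SAP does not state the mapping. Under any mapping, four variables exceed the three scheduled visits, so at least one has no scheduled data.

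**The case against.** The strongest reply concerns weight. Study success rests on the primary t-test, the AAS contains no imputed values, and neither imputation run has a decision rule. The largest equal-missingness shift shown is 0.012 logMAR, about half the standard error of 0.18·√(1/130 + 1/104) = 0.0237. Power at -0.108 with 130/104 is still 0.995. The usual direction is conservative for a superiority claim, and reversal needs a Visit 3A effect that no document suggests. The unimputed t-test can itself serve as the MAR reference. All of this stands and limits the consequence. It does not make the run correct: the SAP does not present it as conservative, and its agreement with the t-test when imputed within arm shows what it ought to return.

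A second reply is that near-coincidence of the two runs needs equal missing fractions. That is right. With no other DCIVA and 10% missing in the test arm and 2% in control, the first run gives -0.1131 and the control-based run -0.1080; with 2% and 10% they give -0.1121 and -0.1176. The gap of about 0.005 is visible, but the first run is still biased in both cases.

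A third is that this is abbreviated pseudo-code; the GLM steps after imputation, for example, do not repeat the first-eye filter. However, the SAP says the code will be used, and no legible text supplies the missing term.

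**Conclusion.** The concern holds. As written, Sensitivity Analysis 1 gives a biased lens contrast under its own MAR assumption, and with equal missing fractions it is a poor reference for the control-based run. Over the ranges shown, the bias is at most 0.012 logMAR, a tenth of the planned difference, and usually toward zero. It is 0.0032 to 0.0076 at 10% missing when Visit 3A is observed with the same effect and a correlation of 0.3 to 0.7. The 10% is an upper-end illustration: the protocol's 10% loss leads to "234 subjects to successfully complete the final study visit (Visit 5A"), which is later than Visit 4A; subjects discontinued before successful implantation are outside the AAS; and the SAP expects missing data to have minimal influence. The missing fraction, correlation and Visit 3A effect are assumptions.

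The variable-list problem also holds, with the reservation that the suffix-to-visit mapping is inferred from DCIVA4. The primary test and its conclusion are untouched; only the two supportive runs are affected.

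**What to change.** - In Sensitivity Analysis 1, run the imputation BY `LENS_MODEL`, or add `LENS_MODEL` to CLASS and VAR.
- In both runs, restrict VAR, the `mu0` values and, in the second, the MNAR list to DCIVA visits that are measured: 3A and 4A, plus 5A where available.
- If 5A is used, say how this works for the Month 3 analysis, because that lock comes before all subjects reach Visit 5A.
- State in SAP 4.6 which visit each DCIVA suffix denotes.

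The cost is a few lines of SAP code, with no new data.

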4.7 Interim Analysis for Efficacy

Not Applicable.

5 Safety Analysis Strategy

5.1 Safety Endpoints

The safety assessments are:

- Adverse Events

- █ [REDACTED]
- █ [REDACTED]
- █ [REDACTED]
- █ [REDACTED]
- █ [REDACTED]
- █ [REDACTED]
- █ [REDACTED]
- █ [REDACTED]
- █ [REDACTED]
- █ [REDACTED]
- █ [REDACTED]
- █ [REDACTED]

5.2 Safety Hypotheses

There are no formal safety hypotheses in this study. The focus of the safety analysis will be a comprehensive descriptive assessment of safety endpoints listed in Section 5.1.

5.3 Statistical Methods for Safety Analyses

Except otherwise stated, the analysis set for all safety analyses is the safety analysis set as defined in Section 2.2. Baseline will be defined as the last measurement prior to exposure to investigational product, except otherwise stated.

5.3.1 Adverse Events

All information obtained on adverse events (AEs) will be displayed by treatment and subject.

The number and percentage of all ocular adverse events, including secondary surgical interventions (SSIs) for either eye, will be tabulated by preferred term with a breakdown by treatment, separately for first and second eyes. An eye with multiple ocular AEs of the same preferred term is only counted once toward the total of this preferred term.

The number and percentage of all adverse events will also be tabulated with a breakdown by treatment, separately for first and second implanted eyes.

Adverse events will be summarized in the following tables:

1. All Adverse Events (Serious and Non-Serious Combined)
 - a. Ocular
 - b. Non-Ocular
2. All Adverse Device Effects
 - a. Ocular
 - b. Non-Ocular
3. All Serious Adverse Events (including Serious Adverse Device Effects)
 - a. Ocular
 - b. Non-Ocular
4. Subject Listings
 - a. Non-Serious Ocular
 - b. Non-Serious Non-Ocular
 - c. Serious Ocular
 - d. Serious Non-Ocular

In addition, descriptive summaries (counts and percentages) for specific AEs will be presented by IOL group. The one-sided exact 95% lower confidence limit of incidence rates (proportion of eyes with events) observed for each IOL group will be compared to the cumulative and persistent adverse event SPE rates. In addition to SPE rates predefined in IS EN ISO 11979-7, the rate of adverse events that may be specifically related to ACRYSOF IQ EDF IOL design features; and any other significant events will be provided. These rates will be accompanied by two-sided exact 95% confidence intervals.

Table 5-1 Adverse Event Safety and Performance Endpoint Rates

Adverse Event	SPE Rate
---------------	----------

	(%)
Cumulative	
Cystoid Macular Oedema	3.0
Hypopyon	0.3
Endophthalmitis ^a	0.1
Lens dislocated from posterior chamber	0.1
Pupillary block	0.1
Retinal detachment	0.3
Secondary surgical intervention ^b	0.8
Persistent	
Corneal stroma oedema	0.3
Cystoid macular oedema	0.5
Iritis	0.3
Raised IOP requiring treatment	0.4

^a Endophthalmitis is defined as inflammatory reaction (sterile or infectious) involving the vitreous body.

^b Excludes posterior capsulotomies.

SPE = Safety and Performance Endpoint

SPE rates are from Table B.2 – Posterior Chamber

IOL Adverse Event Rates in IS EN ISO11979-7:2014.

[Redacted text block]

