12.3.2 Persistent Serious Adverse Events

- Corneal stromal edema
- Cystoid macular edema
- Iritis
- Raised IOP requiring treatment

This list is consistent with the categories provided in I.S. EN ISO 11979-7:2014. A persistent AE is an AE that is present at the conclusion of a clinical investigation per I.S. EN ISO 11979-1. Any other potentially sight-threatening event may also be considered

serious based on the judgment of the Investigator and must be reported appropriately as delineated in Section 12.6.

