13.2 Analysis Data Sets

The primary analysis set for effectiveness analyses will be the all-implanted analysis set (AAS). AAS includes all randomized eyes with successful IOL implantation.

[REDACTED]

- [REDACTED]

- [REDACTED]

- [REDACTED]

The Safety Analysis Set will include all eyes with attempted IOL implantation (successful or aborted after contact with the eye).

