5.4 Interim Analysis for Safety

Not Applicable.

[REDACTED]

[REDACTED]

7 Sample Size and Power Calculations

Effectiveness

The proposed sample size (N = 234; 130 Bilateral EDF IOL and 104 Bilateral Monofocal IOL) provides >99% power for the superiority hypothesis test on mean monocular DCIVA (66 cm) when tested at the 0.025 level of significance (one-sided). This assessment assumes:

- Difference in DCIVA (66 cm) [logMAR]: Mean (SD) = -0.12 (0.18)

The proposed sample size provides 74% power for the non-inferiority hypothesis test with respect to mean monocular BCDVA (4 m) when tested at the 0.025 level of significance (one-sided) with a non-inferiority margin of 0.10 logMAR assuming:

- Difference in BCDVA (4 m) [logMAR]: Mean (SD) = 0.04 (0.16)

The proposed sample size provides >99% power for the superiority hypothesis test on mean monocular DCNVA (40 cm) when tested at the 0.025 level of significance (one-sided). This assessment assumes:

- Difference in DCNVA (40 cm) [logMAR]: Mean (SD) = -0.12 (0.18)

The proposed sample size provides 74% power for the non-inferiority hypothesis test with respect to mean monocular mesopic contrast sensitivity value when tested at the 0.025 level of significance (one-sided) with a non-inferiority margin of -0.15 log unit assuming:

- Difference in contrast sensitivity [log unit]: Mean (SD) = -0.02 (0.38)

The expected sample size (N = 131) will provide 84% power, with $\alpha=0.025$, 1-sided, to detect a difference of 25% in proportion of subjects who respond “Never” to Q1 and Q3 of the spectacles use questionnaire, respectively, assuming

- Proportion of subjects who respond “Never” is 50% in the ACRYSOF IQ EDF IOL group.

Approximately 260 subjects will be randomized to achieve 234 subjects who complete the study, assuming a 10% drop-out rate. It is expected that approximately 131 subjects will respond to spectacle use questionnaire in this study.

Adverse Events

For any event where zero incidence is observed in 130 operative eyes with ACRYSOF IQ EDF IOL, the one-sided exact 95% upper confidence limit is less than 2.3%. Thus, with 95% confidence the true adverse event rate is less than 2.3%.

8 References

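### By default, persistent adverse event rates are divided by all eyes with attempted implantation, so eyes lost before the end with unknown status count as event-free and the rates compared with the SPE limits are biased slightly low

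*SAP*

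**What the plan says.** SAP 5.3 sets a default: "Except otherwise stated, the analysis set for all safety analyses is the safety analysis set as defined in Section 2.2". Protocol 13.2 defines that set as every eye in which implantation was attempted, including implantations aborted after the lens touched the eye.

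SAP 5.3.1 then gives one rule for all rows of Table 5-1: "The one-sided exact 95% lower confidence limit of incidence rates (proportion of eyes with events) observed for each IOL group" is compared with the cumulative and persistent SPE rates alike. The four persistent rows are corneal stroma oedema (0.3%), cystoid macular oedema (0.5%), iritis (0.3%) and raised IOP requiring treatment (0.4%). No separate denominator for them is visible.

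Protocol 12.3.2 defines persistence by end status: "A persistent AE is an AE that is present at the conclusion of a clinical investigation per I.S. EN ISO 11979-1".

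The primary safety objective (Protocol 7.4, SAP 1.1) is set at Month 3/Visit 4A. Protocol 9 expects 260 subjects randomised and 234 completing Visit 5A, with 130 of those in the EDF arm. SAP 5.2 states that safety has no formal hypotheses and will be assessed descriptively.

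**The concern.** A cumulative event can be observed at any visit, so all eyes with attempted implantation is a sound denominator for those rows. A persistent event depends on the eye's state at the end. When a subject leaves early and the end state is unknown, the eye cannot add to the numerator but stays in the denominator. In effect it is imputed as free of the event.

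That error has one direction: it lowers the persistent rate and its confidence limit. The comparison already flags a row only when the lower limit lies above the SPE rate, and dilution makes a flag less likely still. Being no worse than the SPE rates is the primary safety objective, so the denominator should match the definition of the event.

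The documents also leave open what counts as the conclusion of the investigation for the Month 3 report, and whether an event still open at early exit counts as persistent.

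**Working it through.** **The plan's own figures.** SAP 7 gives a precision statement: "For any event where zero incidence is observed in 130 operative eyes with ACRYSOF IQ EDF IOL", the one-sided exact 95% upper limit is below 2.3%. Check: 1 − 0.05^(1/130) = 2.278%, which agrees. Dropout: 260 × 0.9 = 234. At 5:4, EDF subjects randomised are 260 × 5/9 = 144.4, and EDF completers are 234 × 5/9 = 130. The precision figure therefore rests on the planned completers. With 144 eyes the limit would be 1 − 0.05^(1/144) = 2.06%.

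**Relative shortfall.** If no leaver's event is captured and leavers have the same risk as completers, shortfall = 1 − (subjects assessed / subjects in the set).

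- All dropout after implantation: 1 − 234/260 = 10.0%.
- A share of the 26 dropouts leaving before surgery, and so never entering the safety set: 25% gives 1 − 234/253.5 = 7.7%; 50% gives 1 − 234/247 = 5.3%; 75% gives 1 − 234/240.5 = 2.7%.
- All dropout after implantation, but end status captured for half of the leavers: 1 − (0.9 + 0.05) = 5%.
- Leavers at twice the completers' risk (an illustration; the documents give no figure): the true rate is (0.9 + 0.1 × 2) = 1.1 times the completers' rate, and the reported rate is 0.9 times it. The shortfall is 1 − 0.9/1.1 = 18%. Using assessed eyes alone would still leave 1 − 1/1.1 = 9%.

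**Effect on the SPE comparison.** One-sided exact 95% lower limit for x events in n eyes: the 5% quantile of Beta(x, n − x + 1). A row is flagged when this limit exceeds its SPE rate. Pooling both eyes is an assumption: 2 × 144.4 = 289 attempted and 2 × 130 = 260 assessed.

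| EDF eyes | Events | All attempted: rate (lower limit) | Assessed: rate (lower limit) |
|---|---|---|---|
| First eyes, 144 v 130 | 1 | 0.69% (0.036%) | 0.77% (0.039%) |
| | 2 | 1.39% (0.247%) | 1.54% (0.274%) |
| | 3 | 2.08% (0.570%) | 2.31% (0.632%) |
| | 4 | 2.78% (0.954%) | 3.08% (1.058%) |
| Both eyes, 289 v 260 | 3 | 1.04% (0.284%) | 1.15% (0.315%) |
| | 4 | 1.38% (0.474%) | 1.54% (0.527%) |

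First eyes: two events stay below 0.3% and three exceed 0.5% with either denominator, so the flag appears at three events for SPE 0.3%, 0.4% and 0.5% alike. Control first eyes (116 v 104) are also unchanged: two events for 0.3%, three for 0.4% and 0.5%.

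Both EDF eyes pooled: the flag changes at exactly 3 events for SPE 0.3% and at exactly 4 events for SPE 0.5%. It does not change for 0.4%, where four events are needed either way. If half of the dropouts leave before surgery, the pooled set is 2 × 247 × 5/9 = 274 eyes. The 0.5% reversal then disappears (lower limit 0.5002% at 4 events), while the 0.3% reversal remains.

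**The case against.** The strongest reply has five parts.

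1. *The denominator is inferred from a default that allows exceptions.* The body of SAP 2.2 and the text after Table 5-1 are not visible. This stands: an exception in redacted text cannot be ruled out, and the point rests on the visible rule.

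2. *Leavers' events are not lost by design.* A reader might infer that a persistent event can be seen only in eyes examined at the last visit. The documents do not support that. Adverse events are scheduled at Early Exit (Protocol 5), and events ongoing at exit are updated up to database lock (12.8). But the Early Exit visit is only recommended (11.8) and depends on the subject being willing and able (11.11.2), and no visible rule says whether an event open at exit counts as persistent. The bias applies to eyes whose end status stays unknown.

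3. *Ten per cent is not a bound.* It covers everyone randomised through Visit 5A, including those who leave before lens contact. Fewer will have left by Month 3. It could also be exceeded if leavers fare worse. This stands, so 10% is one scenario in a range.

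4. *The flags barely move.* SAP 5.3.1 tabulates adverse events separately for first and second eyes, and the sentence on SPE rates does not state pooling. Without pooling, no first-eye flag changes. This stands.

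5. *The benchmark's own denominator is unknown.* The documents do not say whether the ISO rates were built on implanted or assessed eyes. This also stands. The argument therefore rests on the protocol's definition of persistence, not on how the SPE rates were derived.

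**Conclusion.** The point holds as a minor one. Under the visible rules, eyes with unknown end status are counted as free of persistent events, so those rates are biased low. The relative shortfall is about 10% if all planned dropout follows implantation and about 5% if half precedes surgery, given that no leaver's event is captured and leavers have completers' risk. In EDF first eyes that is about 0.07 percentage points for one event (0.77% − 0.69% before rounding).

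A reader might infer that this decides whether the lens meets the SPE rates. The documents do not support that. The comparison is descriptive, first-eye flags are unaffected, and a reversal needs pooled EDF eyes and exactly 3 or 4 events. Nor does the use of 130 eyes in the precision statement show that the sponsor intended an assessed-eye denominator: that figure is given for any event and may simply be a cautious planning number.

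**What to change.** In SAP 5.3.1 and Protocol 13.7:

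- Keep the safety set for the cumulative rows.
- For the four persistent rows, use as denominator the eyes examined at the visit that defines persistence for that report: Visit 4A for the Month 3 analysis and Visit 5A for the final analysis. A Visit 5A denominator alone would not serve the primary safety objective, which is set at Month 3.
- Add eyes that left early with one of these events ongoing, counted as persistent in numerator and denominator. This addresses leavers with unresolved events. It leans against the lens, because leavers who were clear at exit are not added and some open events may have resolved.
- Show the safety-set rate as a supplement, and print the number of eyes assessed beside each rate.

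The cost is wording in two sections, one denominator in a table program and slightly more table work. No new data are needed. The persistent rates become slightly less favourable to both lenses.
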